## **Lab Clinical Deterioration and Suicidality Standard Operating Procedure (SOP) Version date: January 20th, 2021**

### **Procedures during partial hospitalization (while patient attends BHP)**

All participants in this study will be receiving intensive partial hospital treatment during the acute phase of the study. Therefore, deterioration or suicide risk during this phase will be reported to the patient's clinical team manager at the BHP. At that point, the treatment team will manage the safety of the patient and determine whether inpatient hospitalization is required.

We will maintain regular communication with the patients' treatment team throughout the course of their partial hospital stay. [name] office is in the same hallway as all of the BHP clinical team managers and psychiatrists. We will use the BHP's confidential voicemail system for non-urgent information and pagers for urgent clinical information.

#### ***Clinical Deterioration***

As part of standard clinical care, the BHP's Progress Monitoring Coordinator (PMC) will monitor depression symptoms daily, via use of the PHQ-9 using RedCap. As part of standard clinical care, the PMC will notify the clinical team manager of any patient who experiences an increase of 5 or more points on the PHQ-9 from the baseline assessment. At that point, the treatment team will manage the safety of the patient and determine whether inpatient hospitalization is required. Each time the PHQ-9 total score increases by 5 or more points, the PMC will again notify the clinical team manager of the symptom increase.

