### **Phase 2: Open Trial (Enrollment COMPLETE)**

We will enroll 16 participants meeting the following inclusion criteria.

**Inclusion criteria:** a) currently receiving partial hospital care at the study site; b) age  $\geq 18$ ; c) at least moderate symptom severity (PHQ-9 or GAD-7 score  $\geq 10$ ); d) no current psychiatric symptoms that would prevent informed consent or understanding of research procedures (e.g., active symptoms of psychosis, mania), e) no current/active suicidal ideation (PHQ-9 item 9  $> 1$ ) and f) signing a release of information for treatment providers is an inclusionary requirement for study participation. Consistent with the RDoC, DSM-5 diagnosis will not affect eligibility. We anticipate a range of primary diagnoses, principally mood and anxiety disorders. Participants will be selected based on their baseline level of interpretation bias. Only patients who exhibit at least a minimal level of interpretation bias ( $< 80\%$  accuracy on the WSAP) will be offered participation.

**Source of subjects.** The Behavioral Health Partial Hospital Program (BHP) at McLean Hospital admits over 850 individuals per year. The PI is Assistant Director of Research and a staff psychologist at the BHP, and [name] (Co-I) is Director. The BHP delivers group and individual CBT to patients with a range of psychiatric disorders, primarily mood, anxiety, personality, and psychotic disorders. Treatment focuses on concepts such as self-monitoring, cognitive restructuring, and behavioral activation. The average length of stay is 8 days. Patients are assigned a case manager, psychiatrist, and skills coach.

**Recruitment methods.** Study staff will review partial hospital patients' scores on the PHQ-9 and GAD-7 to determine initial eligibility. On patients' second day at the BHP, study staff will offer participation to those who score above the cut-offs. Interested patients will complete the interpretation bias assessment to determine eligibility. Patients may also express interest to study staff via flyers posted at the BHP.

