### **Phase 3: Randomized controlled trial.**

In this Randomized Control Trial, we will recruit 64 partial hospital patients. All inclusion and exclusion criteria, sources of subjects, and recruitment methods are the same as detailed in the Phase 2: Open Trial, except that current/active suicidal ideation criteria will be removed, such that individuals with all scores for phq9 item 9 are eligible. Further, after reaching our initial recruitment goal of 64, we will continue to recruit those participants that identify as BIPOC in order to achieve our proposed percentage of BIPOC participants.

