**Procedures for Proposed Protocol:**

The research coordinator or another member of the study staff will approach potentially eligible patients (scoring above a 9 on PHQ-9 or GAD-7) on their second day in the program and inform them about the study, and send them a brief screening survey to assess initial eligibility prior to study consent and enrollment (i.e., owns an iPhone, willing to sign a release of information for outpatient providers, willing to use the app per protocol and willing to complete follow-up assessments). If patients are eligible based on this initial screening questionnaire, they will then receive a detailed description of the study procedures, risk, and benefits and will review a study fact sheet for remote consent with trained study staff. Additionally, those patients who did not originally consent to the BHP main study, will have to consent to the main study in order to be eligible for the RCT. They will then complete the interpretation bias assessment to determine eligibility to participate in the trial.

On patients' second day at the BHP, staff will offer participation. Interested patients will complete the eligibility assessment. Study staff will immediately review scores on the measure of interpretation bias (WSAP; see Measures) to determine eligibility. If eligible, they will complete the remaining pre-assessment measures. If ineligible, patients will be compensated and continue with treatment as usual at the BHP. After the eligibility session, patients will be randomized into either HabitWorks or Symptom Tracking groups by the PI.

The PI will train research staff to orient patients to HabitWorks and Symptom Tracking conditions and reinforce the rationale and instructions provided in instructional videos.

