The overall risk of possible ineffective intervention will be minimized by: 1) frequent monitoring (daily for all study participants); 2) allowing study participants to receive standard partial hospital level of care or outpatient care, including pharmacotherapy and psychotherapy; 3) reminding all participants at each contact of the emergency numbers they should call if they experience a significant worsening of symptoms and/or suicidal ideation; and 4) the study protocol specifying that, in the event of clinical deterioration of anxiety or depression symptoms, or increased suicidality, study subjects will be evaluated by a licensed clinician.

To minimize risk of clinical deterioration of anxiety and/or depression, a protocol for close clinical monitoring has been established.

See SOP. In brief, we will not be monitoring symptoms and suicide risk via app surveys AT ALL throughout the study. Patients will be reminded multiple ways that they should not use study surveys as a means to communicate a need for clinical attention (see Lab SOP). If they are in distress they may reach out to outpatient providers or emergency services. As part of TAU, patients will create a safety plan with their providers at the time of discharge from the program and research staff will go over this plan with them, as another reminder of what to do in cases of emergency, as we are not following them. Upon discharge from the BHP, we will also be providing participants with a contact list for local crisis services throughout the state, and helping participants identify a few resources they could use. Participants will be reminded before each survey that they may skip the survey or stop the survey at any time, and that they should reach out to outpatient providers, suicide crisis numbers, or 911 in case of emergencies.

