### **VIII. POTENTIAL BENEFITS**

Potential benefits to all participants include a detailed psychiatric evaluation and increased assessment and monitoring of their anxiety and depression symptoms. If a participant's anxiety or depression worsens substantially, we will provide feedback to the partial hospital treatment team (acute phase). If the participant is at risk for a suicide attempt, we will take immediate action to safeguard that patient. All participants may also benefit from the opportunity to practice self-assessment skills (i.e., symptom tracking). We believe that serious risks (e.g., loss of confidentiality or major psychological distress due to study participation) to subjects are very unlikely. We have attempted to minimize these risks (as described above). While some risks may be more likely to occur (e.g., minor, transient psychological distress), these risks are much less serious. Therefore, the potential benefits of the proposed study seem to outweigh the potential risks of this study for the individual participants.

The overall goal of this research project is to learn more about the development of efficacious and easily disseminated treatments for SMI, thus, indirectly, all participants may eventually benefit from furthering science in this field, as may other individuals who suffer from these disorders.

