### **Documentation**

Study staff will document each time a participant is identified for clinical deterioration or suicidality. Documentation will include the following:

- Date of identification
- Reason for identification (e.g., increase on GAD-7)
- Date and time clinician contacted
- Outcome

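### Patients can enter on the GAD-7 alone and the protocol promises action if anxiety worsens, but no SOP rule requires notification on an anxiety measure

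*Protocol*

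**What the plan says.** **Entry.** The open-trial inclusion criteria (Protocol, Subject Selection, Phase 2) ask for "at least moderate symptom severity (PHQ-9 or GAD-7 score" of 10 or more). The RCT carries this over: "All inclusion and exclusion criteria, sources of subjects, and recruitment methods are the same as detailed in the Phase 2: Open Trial", apart from the suicidal-ideation criterion and the later restriction of additional recruitment. The RCT procedures in section V likewise approach patients "scoring above a 9 on PHQ-9 or GAD-7".

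**What is promised.** Section VII, under minimizing the risk of ineffective intervention, says that "in the event of clinical deterioration of anxiety or depression symptoms, or increased suicidality, study subjects will be evaluated by a licensed clinician". It adds that a close-monitoring protocol exists for anxiety and/or depression and sends the reader to the SOP. Section VIII says that if a participant's "anxiety or depression worsens substantially, we will provide feedback to the partial hospital treatment team", and limits this to the acute phase.

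**What the SOP does.** Its Clinical Deterioration section has the progress monitoring coordinator follow depression symptoms daily and notify the clinical team manager of "any patient who experiences an increase of 5 or more points on the PHQ-9 from the baseline assessment". Repeat notification also depends on the PHQ-9 total. The Documentation section, at the end of the same SOP, lists what staff must record, including "Reason for identification (e.g., increase on GAD-7").

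**What data exist.** The Measures section says that patients complete both the PHQ-9 and the GAD-7 daily as part of standard care.

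**The concern.** The protocol treats anxiety and depression alike when it admits patients and when it describes how they are protected. The SOP, which is meant to put that protection into practice, specifies a trigger for depression only. A participant who qualified on anxiety has no criterion attached to the symptom that brought them in. The SOP also disagrees with itself: its Documentation section expects staff to record a GAD-7 increase as a reason for identification, but none of its procedures produces one.

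Clinical deterioration is among the risks listed in section VII, and the statements in sections VII and VIII support the protocol's account of risk and benefit. If staff follow the SOP as written, whether a worsening of anxiety is acted on depends on judgement rather than on a stated duty. The documentation of identified cases need not capture anxiety worsening consistently.

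**Working it through.** No sample size, power or event-rate calculation bears on this point. The check sets the SOP's triggers beside the promises.

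| SOP section | What prompts action by staff | Anxiety measure used? |
|---|---|---|
| Clinical Deterioration, in hospital | PHQ-9 total up by 5 or more from baseline; notified again at each such increase | No |
| Suicidality, in hospital | PHQ-9 item 9 up from baseline; a yes to C-SSRS question 4 or 5 | No |
| After discharge, weekly check-ins and EMA | Nothing: staff do not review these surveys on any scale | No |
| Suicidality, 1 and 3 months | A yes to C-SSRS question 4 or 5 | No |

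**Step 1: can a patient enter on anxiety alone?** Yes. The entry criterion joins the two scales with an or, so a PHQ-9 below 10 with a GAD-7 of at least 10 satisfies it.

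**Step 2: can anxiety worsen without meeting any trigger?** Yes. A hypothetical in-hospital case:

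- GAD-7 goes from 12 to 20, a rise of 20 − 12 = 8.
- PHQ-9 goes from 7 to 11, a rise of 11 − 7 = 4, which is below 5.
- Item 9 does not rise, and C-SSRS questions 4 and 5 are not answered yes.

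This patient qualified on the GAD-7 (12 is at least 10; the PHQ-9 of 7 is not). No row of the table is met, yet the course could fall within the anxiety wording of sections VII and VIII. It also matches the Documentation example.

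**Step 3: could the Documentation example arise from another rule?** No stated trigger yields it. The in-hospital rules use the PHQ-9 and the C-SSRS, post-discharge surveys are not reviewed, and the follow-up rule uses the C-SSRS.

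**Step 4: what kind of conflict is this?** Sections VII and VIII make a promise for which the SOP has no specific rule, which is an omission. The SOP's Documentation and Clinical Deterioration sections do not fit each other, which is an inconsistency within one document.

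**Step 5: which phase is affected?** The acute phase. After discharge the protocol deliberately leaves symptom surveys unreviewed for depression and anxiety alike.

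**The case against.** The strongest reply is that the PHQ-9 rule is not the only route to the treatment team.

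- The SOP's opening paragraph on the partial hospital stay says that deterioration will be reported to the clinical team manager. It does not confine this to the PHQ-9, and it promises regular communication with the team.
- Section V says that the progress monitoring coordinator passes self-report data to treatment teams. It also says that self-report scores are highlighted for team managers under the existing hospital protocol, although the questionnaire described there is given at registration and discharge.
- The SOP's Suicidality section counts the clinical team manager among the licensed clinicians, so a report to that person could lead to the evaluation promised in section VII.

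This reply stands in part. A reader might infer that worsening anxiety would never be identified, or that the safeguard does not operate for patients who entered on anxiety. The documents do not support either reading, because these general routes could carry a GAD-7 rise to the team. They do not close the gap, however: none states an anxiety criterion or a duty to notify. For depression the SOP did not rely on general transmission but added an explicit rule.

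A second reply is that the PHQ-9 rule describes the hospital's standard care rather than a study procedure. That bears on the cost of change. It does not remove the mismatch, since section VII cites this SOP as the monitoring protocol for both symptoms.

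A reader might also infer that an adverse effect of the intervention on anxiety could go unseen. That goes too far. The GAD-7 is scheduled in both arms from baseline to 3 months. The SAP's Phase 3 section plans between-group effect sizes with 95% confidence intervals, though it does not name the GAD-7. The DSMB reviews adverse events under a broad definition, and nothing in the documents makes the identification record an outcome or a harm analysis.

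**Conclusion.** The point holds as a gap in the acute phase. The SOP has no explicit anxiety criterion and no duty to notify on anxiety worsening, while sections VII and VIII promise action on it and the SOP's own Documentation section assumes that it can be identified. It is more than missing detail, because the deterioration rule followed as written does not carry out a safeguard that the protocol says is in place.

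The size cannot be given. The documents do not report how many patients qualify on the GAD-7 alone, or how often anxiety worsens without a PHQ-9 rise of 5, an item 9 increase or a C-SSRS trigger. The worked case shows only that such a course is possible. No harm is shown, and it does not follow that the risk-benefit statement is wrong for these participants. The conclusion assumes that the SOP reproduced with the protocol is the complete one to which section VII refers.

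**What to change.** The investigators should reconcile four places: section VII (minimizing the risk of ineffective intervention), section VIII, and the SOP's Clinical Deterioration and Documentation sections. Afterwards, the SOP's deterioration procedure and the protocol's statements about anxiety should cover the same symptoms, and the documentation example should be one that the procedure can produce. Whether the procedure, the statements or both change is for the responsible clinicians; no threshold or clinical rule is proposed here.

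The cost is rewording of the SOP and protocol, and coordination with the hospital, because the current rule belongs to its standard-care process. Depending on what the clinicians decide, there may be some additional notifications to team managers. No new data collection is needed, since the GAD-7 is already completed daily.

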#### ***Suicidality***

As part of standard clinical care, the PMC will monitor suicidal ideation daily, via use of item 9 on the PHQ-9 using RedCap. As part of standard clinical care, the PMC will notify the clinical team manager of any patient whose experiences an increase from the baseline assessment (e.g., from a 0 to 1, from a 1 to 2, etc.). At that point, the treatment team will manage the safety of the patient and determine whether inpatient hospitalization is required. Each time item 9 on the PHQ-9 increases by one or more points, the PMC will again notify the clinical team manager of the symptom increase.

As part of standard clinical care, patients complete the Columbia Suicide Severity Rating Scale upon admission to the BHP. As part of this study, they will also complete it at post-BHP treatment. Answers of "Yes" to questions 4 or 5 on C-SSRS will result in emergent evaluation by licensed clinician (either BHP clinical team manager or [name]). During periods where the BHP is operating remotely, participants will complete the self-report version of the C-SSRS during study assessments. In these instances, study staff will monitor their responses in real-time, and will ensure that a licensed clinician is available at time of study assessment for emergent evaluation if necessary (Answers of "Yes" to questions 4 or 5).

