### Measures.

Participants will complete measures that are already administered as part of standard clinical care at the BHP.

The Mini International Neuropsychiatric Interview (MINI) is a structured interview assessing for DSM-V Axis I disorders. The MINI will be administered by doctoral practicum students and interns in clinical psychology who will receive weekly supervision by the post-doctoral fellow.

The PHQ-9 is a brief self-report questionnaire assessing symptoms of depression. Patients complete the PHQ-9 at daily.

The GAD-7 is a brief self-report questionnaire assessing symptoms of anxiety. Patients complete the GAD-7 daily.

The Quality of Life Enjoyment and Satisfaction Questionnaire (Q-LES-Q) will assess satisfaction and quality of life.

To assess suicidal ideation and behaviors (lifetime, past month), we will use the interview administered *Columbia Suicide Severity Rating Scale* (CSSRS). During remote assessments, when clinical interview is not possible, we will use an adapted form of the CSSRS as a self report measure.

Participants in proposed study will complete the following additional measures:

WSAP. Word-sentence pairs representing benign or negative interpretations are presented, and patients decide if they are related or not. In the assessment version of this task, no feedback is given about the accuracy of participants' responses. The task will record reaction times for 4 WSAP trial types (endorse benign, reject benign, endorse negative, reject negative), reflecting the relative speed or ease with which participants make interpretations. We will

calculate reaction time bias scores for each trial type (negative vs. benign). The task will also record participants' responses (yes/no) for each trial type (negative vs. benign) to allow calculation of the percentage of negative and benign interpretations endorsed. In the case of remote recruitment in phase 2b and 3, the assessment version of the WSAP will be used as a screening tool prior to the Pre-treatment.

Schedule of Assessments	Pre	Daily	Post	1-mo	3-mo
Interviews					
MINI	X				
CGIS			X	X	X
WSAS	X		X	X	X
Longitudinal Interval Follow-Up Eval				X	X
Qualitative Exit Interview (open trial and first 20 in RCT)				X	
CSSRS	X			X	X
App or Computer Delivered					
*The HabitWorks app will deliver all daily surveys. Redcap will be used to deliver computerized surveys during in-person assessments.					

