Demog. Form, CEQ	X				
PHQ-9; GAD-7	X	X	X	X	X
Q-LES-Q, BHS, CFI, MPS, GSE	X		X	X	X
Exit Questionnaire				X	
WSAP	X	X	X	X	X
Scenario Recognition Task				X	
EMA PANAS	X	X	X	X	X
CSSRS- Self Report	X			X	X
System Usability Scale- HW condition				X	
TWEETS- HW condition				X	

The Scenario recognition task is the most widely used assessment of interpretation bias in CBM- and will ensure that effects are not solely attributable to practice or method effects. In brief, participants first read 10 ambiguous scenarios and a comprehension question to ensure they actually read the scenario. In the second phase, participants read the title of the ambiguous scenario followed by four versions of the final sentence presented in a random order. Sentences represent a) a possible positive interpretation, b) a possible negative interpretation, c) a positive foil, and d) a negative foil.

Participants rate each sentence for its similarity in meaning to the original story using a 4-point scale ranging from 1 (very different in meaning) to 4 (very similar in meaning). We will calculate the average similarity rating for negative and positive interpretations.

Co-primary clinical outcomes will include stake-holder relevant measures of global improvement and functioning. The PI will train study staff to administer these brief scales and will monitor reliability using established procedures at the BHP.

Clinician-administered Clinical Global Improvement Scale (CGIS) to assess global improvement.

Clinician-rated 5-item Work and Social Adjustment Scale (WSAS) to assess interference caused by the patient's symptoms in the domains of work, home management, leisure, and family relationships.

Other self-report measures will include:

Credibility Expectancy Questionnaire to assess patients' beliefs about the treatment expectancy (affectively based) and treatment rationale credibility (cognitively based).

Exit Questionnaire to assess patients' satisfaction with the treatment provided.

Beck Hopelessness Scale (BHS) to assess negative attitudes about the future.

Cognitive Flexibility Inventory: The Cognitive Flexibility Inventory is a measure of mental flexibility and assesses the degree to which individuals are able to replace maladaptive thoughts with adaptive ones and maintain a balanced mindset.

15-Item Multidimensional Perfectionism Scale (short form): The MPS is a widely used self-report measure of perfectionism.

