#### **Safety Plan.**

See Lab SOP attached.

The DSMB will review rates of adverse events to determine any changes in participant risk. A brief report will be generated quarterly for the study record and forwarded to the DSMB and annually to the Partners Healthcare Institutional Review Board. The DSMB members will be available to meet outside of the quarterly meetings, if necessary, to discuss concerns regarding a particular participant or research problem. If necessary, they will make appropriate recommendations for changes in protocol. The PI will meet weekly with study staff to review experiences with participants. All adverse events will be reported to the IRB per PHRC

guidelines: [https://partnershealthcare-public.sharepoint.com/ClinicalResearch/Reporting\\_Unanticipated\\_Problems\\_including\\_Adverse\\_Events.pdf](https://partnershealthcare-public.sharepoint.com/ClinicalResearch/Reporting_Unanticipated_Problems_including_Adverse_Events.pdf). The DSMB will inform NIH of any significant action taken as a result of DSMB findings. This study will use the NIH's Common Adverse Events (AEs) and Serious Adverse Events (SAEs) definitions for clinical research. Adverse events are defined as any event or outcome that has resulted in harm to the participant, has affected the participant detrimentally, has worsened as a result of participation in the study, or that has resulted in increased risk to the participant or others whether or not the risk actually results in harm.

In the event that a participant either withdraws from the study or the investigator decides to discontinue a client due to SAE, the participant will be monitored by the PI via ongoing status assessment until 1) a resolution is reached i.e., the problem requiring hospitalization has resolved or stabilized with no further changes expected; 2) the SAE is determined to be clearly unrelated to the study intervention; or 3) the SAE results in death. Unexpected events are defined as any event or outcome that was not described as a risk of participation in the research, or though described as a risk, the event or outcome has occurred with unexpected severity or frequency.

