### **Procedures following partial hospitalization (post-discharge from BHP)**

At discharge as part of treatment as usual participants will create a safety aftercare plan with their BHP provider, and this plan will be gone over in their discharge session with research staff. In addition, staff will provide participants with a list of local crisis resources across the state, and ask participants to identify a few they could contact if needed. In this session we will reiterate that the research team will not be checking patients Weekly Check-Ins (PHQ/GAD) or the EMA surveys. Following discharge from the hospital, patients are expected to follow their aftercare plan with outpatient providers. During this time study staff will not be monitoring safety of any Mood Check ins completed by participants, nor will they be following the daily EMA surveys.

The smart phone app will clearly remind patients as they complete these forms each day that study staff will not see the data and thus, if they feel that they need attention, they should call their outpatient

providers, call 911, use the crisis text hotline, or go to their local Emergency Department. Additionally, if a patient indicates any level of suicidal ideation on the PHQ-9 (item 9 score  $\geq 1$ ), the app will generate a message urging the patient to call their outpatient providers, contact emergency services, or utilize the crisis text line if they are feeling unsafe. Additionally, the list of crisis resources provided to patients upon discharge will be available to view in the app FAQs.

Additionally, any symptom monitoring surveys completed in the Long Term phase will not be monitored at all by staff.

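### The Lab SOP requires a study C-SSRS at the end of partial hospital treatment, but both C-SSRS rows of the Schedule of Assessments leave Post blank

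*Protocol*

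**What the plan says.** The Lab SOP, under procedures while the patient attends the partial hospital (BHP), has a Suicidality section. It treats the admission C-SSRS as standard care and then adds: "As part of this study, they will also complete it at post-BHP treatment". A Yes to question 4 or 5 sends the patient to a licensed clinician for urgent evaluation. When the BHP operates remotely, the self-report version is used, with staff watching the answers live and a clinician on hand. The C-SSRS at 1 and 3 months has its own paragraph in the post-discharge part of the SOP.

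The table headed "Schedule of Assessments" in the protocol's Measures section has the columns Pre, Daily, Post, 1-mo and 3-mo. The interview CSSRS row and the "CSSRS- Self Report" row each carry marks at Pre, 1-mo and 3-mo, and nothing at Post.

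On safety, the protocol body points to the SOP. The Safety Plan opens with "See Lab SOP attached", and Risks and Discomforts also refers to the SOP before stating that "we will not be monitoring symptoms and suicide risk via app surveys AT ALL throughout the study".

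**The concern.** Two current parts of one protocol give different instructions about a suicide-risk assessment. A schedule of assessments is the table from which staff usually build visit checklists and database forms. If they do so here, no C-SSRS is collected at the end of the acute phase, and the question 4 or 5 rule has nothing to act on at that visit.

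The timing matters because the next phase is the least supervised. After discharge, study staff do not look at the weekly check-ins or the EMA surveys. The protocol's own background describes the months after discharge as a time of risk.

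The RCT also widened entry: "individuals with all scores for phq9 item 9 are eligible". The daily item 9 safeguard has the coordinator "notify the clinical team manager of any patient whose experiences an increase from the baseline assessment", so it responds to worsening, not to a score that starts high and stays high.

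Aim 3 seeks pilot data on suicidal ideation and behaviors. Under the schedule, the C-SSRS contributes nothing to it at discharge.

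**Working it through.** The plan states no figure to reproduce. The check sets the two texts side by side and counts time points and days.

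**Time points**

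| C-SSRS time point | Lab SOP | Schedule, interview row | Schedule, self-report row |
|---|---|---|---|
| Admission / Pre | yes | X | X |
| End of BHP treatment / Post | yes | blank | blank |
| 1 month | yes | X | X |
| 3 months | yes | X | X |

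After baseline, the SOP gives 3 time points and the schedule 2.

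**Could the mismatch be only apparent?**

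- *Damaged table.* In the same table, the CGIS, WSAS, PHQ-9/GAD-7 and Q-LES-Q rows have a Post mark in its proper place. The two C-SSRS rows sit in different blocks and show the same blank. The columns are intact.
- *The SOP means the follow-up visits.* The sentence is in the section for patients still attending the BHP, and the 1- and 3-month forms are covered separately.
- *Left out as standard care.* The SOP assigns the admission form to standard care and this one to the study. The schedule also lists standard-care measures such as the PHQ-9 at Post.
- *The schedule covers only the open trial.* It has rows for the HabitWorks condition and mentions the first 20 RCT participants. The RCT section keeps the open-trial measures.

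**Days to the next C-SSRS after admission**

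Inputs: acute phase of 1 to 14 days (treatment phase table); average stay of 8 days (Source of subjects). Assumptions: these are calendar days, and the 1-month visit falls 30 days after discharge.

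- Schedule: 1 + 30 = 31 days; 14 + 30 = 44 days; at the average stay, 8 + 30 = 38 days.
- SOP: 1 to 14 days; 8 at the average stay.

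If the stay is counted in attendance days, the calendar gaps are longer.

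**Recall window at Post**

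The Measures section gives the C-SSRS recall periods as lifetime and past month. Taking a month as 30 days, a past-month form at discharge reaches back before admission by 30 − 1 = 29 days at the shortest stay, 30 − 8 = 22 at the average and 30 − 14 = 16 at the longest. More than half of the window lies before treatment in every case.

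**The case against.** The strongest reply is that the patient is not unwatched. The question 4 or 5 rule follows the sentences on both the admission and the end-of-treatment form, so a patient who enters at high risk can trigger it on admission. PHQ-9 item 9 is collected daily and at Post. Self-report scores go to clinical team managers and treatment teams, and the SOP has suicide risk in this phase reported to the team manager; neither route is limited to increases. At discharge the patient makes a safety plan with the BHP provider, and "this plan will be gone over in their discharge session with research staff". Crisis contacts are handed out, and the app shows a warning message for any positive item 9 answer. All of this stands. A reader might infer that patients with a persistently high item 9 score leave unnoticed; the documents do not support that. What remains is that the item 9 alert does not fire without an increase (a score of 2 at baseline and 2 at discharge is a change of 0), and that none of these safeguards is the C-SSRS check promised for that visit.

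A second reply is that the SOP governs safety, so the form is already required and its omission is conjecture. This stands in part: the harm arises only if staff follow the schedule. But a reader cannot be sure that the SOP prevails. It is dated January 2021 and the protocol June 2021, so the form may have been dropped on purpose and the SOP left unrevised. The protocol's deference to the SOP makes a slip in the schedule more likely, but does not prove it.

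A third reply is that no analysis depends on the form. That is nearly right. Aim 3 names no time point, and the SAP's Phase 3 section plans effect sizes with 95% CIs without naming the C-SSRS. With the past-month window, a discharge form would also be a weak measure of the acute phase. The post visit is itself optional in the RCT, so some forms would be missing anyway.

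**Conclusion.** The contradiction is real and should be corrected. It is an inconsistency between documents, with a modest safety consequence. If staff follow the schedule, there are 2 C-SSRS time points after baseline instead of 3, and the first comes about 31 to 44 days after admission (38 at the average stay) instead of 1 to 14. This assumes calendar days and a 30-day interval to the 1-month visit. Because the 1- and 3-month visits are optional in the RCT, a participant who misses both would have no study C-SSRS after baseline under the schedule.

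A reader might want to put a number on the patients missed. The documents do not allow it, since they give no rate of Yes to question 4 or 5. The 70% with moderate or high suicide risk in the pilot is a MINI rating in another sample. The 15% dropout in the SAP's power analysis is an assumption for a later trial, not loss by discharge in this one.

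A reader might also infer that Aim 3 fails. It does not: the loss is one descriptive time point.

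**What to change.** Add a Post mark to the interview C-SSRS row of the Schedule of Assessments. Add one to the self-report row with a note that it applies when the BHP operates remotely, because the SOP limits that version to such periods during the hospital phase. Preferably set the recall period at Post to the time since the last assessment, so that the form describes the stay and is not triggered by ideation from before admission.

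The cost is two table marks, a footnote and one more instrument at a post-treatment visit that already exists and is paid. The SOP already promises the clinician cover.

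If the sponsor removed the end-of-treatment C-SSRS deliberately, correct the SOP sentence instead and state which discharge safeguards are relied on in its place.
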